**Specific Aim 2b Procedure:**

**Outcomes:** We will analyze the actual use of the CDS, defined as interaction with the BPA, signing of orders, or accountable justification documentation within the BPA.

## VI. BIOSTATISTICAL ANALYSIS

Data collected during the pilot study will not be included in the final analysis. Patients enrolled in the pilot study will not be enrolled in the final analysis. However, PCPs in the pilot study will be included in the intervention arm of the main clinical trial. A subgroup analysis will be performed on patients of these PCPs.

Table 1. Outcome Variables and Measures for Both Arms

Measurement Variable	Form of Variable	Analysis Metric	Time Point
Primary			
Mean SBP	Continuous	Change from baseline	6 months, 12 months, 18 months
Secondary			
Controlled SBP Rate	Dichotomous	Proportion of patients with controlled SBP rate	6 months, 12 months, 18 months
Urine Albumin to Creatinine Ratio	Continuous	Urine Albumin to Creatinine Ratio	6 months, 12 months, 18 months
Serum Creatinine > 2.0	Dichotomous	Proportion of patients with Creatinine > 2.0	Monthly
eGFR	Continuous	eGFR	6 months, 12 months, 18 months

Medication ordered	Dichotomous	Proportion of patients with recommended medication ordered	6 months
Basic metabolic panel ordered	Dichotomous	Proportion of patients with basic metabolic panel ordered	6 months
Referral to e-consults	Dichotomous	Proportion of patients with referral to e-consults	6 months
BPA acceptance	Dichotomous	Proportion of patients where BPA was accepted	6 months
Mean SBP of less than 110	Dichotomous	Proportion of patients with mean SBP of less than 110	Monthly
Newly documented allergy	Dichotomous	Proportion of patients with newly documented allergy due to adverse drug events	Monthly
K+ > 5.2	Dichotomous	Proportion of patients with K+ > 5.2	Monthly
K+ < 3.6	Dichotomous	Proportion of patients with K+ < 3.6	Monthly
Mean SBP intent-to-intervene analysis with imputation of missing 6-month BP measurement	Dichotomous	Proportion of patients with missing 6-month BP measurement	6 months
Controlled SBP Rate intent-to-intervene analysis with imputation of missing 6-month BP measurement	Dichotomous	Proportion of patients with missing 6-month BP measurement	6 months

Table 2. Outcome Variables and Measures for Intervention Arm Only

Measurement Variable	Form of Variable	Analysis Metric	Time Point
Acknowledgment reason entered	Dichotomous	Proportion of patients with acknowledgment reason entered	6 months
Feedback button clicked	Dichotomous	Proportion of patients with feedback button clicked	6 months
PCP participation on pledge email survey	Dichotomous	Proportion of patients whose PCPs participated in pledge email survey	6 months
Guideline accessed	Dichotomous	Proportion of patients with guideline accessed	6 months

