**Specific Aim 2 & 2a Procedures:**

**Setting:** The Brigham and Women's Primary Care Practice-Based Research Network (BWPC PBRN) is one of 155 PBRNs nationally certified by the Agency for Healthcare Research and Quality (AHRQ). The BWPC PBRN is a network of 15 practices which includes hospital-based practices, community-based practices, and community health centers affiliated with Brigham and Women's Hospital. The network includes 185 primary care physicians that care for approximately 150,000 patients.

**Subjects:** All patients over the age of 18 who have a visit with a PCP at one of the intervention practices during the 2 years preceding the study period will be eligible. We are able to utilize data from the past five years stored in the EHR to identify CKD patients with uncontrolled HTN. The first inclusion criteria will be CKD, defined as two prior eGFR 16-59 mL/min/1.73m^2 separated by 90 days, as calculated by CKD-EPI, or two prior UACR >30mg/g. The second inclusion criteria will be uncontrolled hypertension, defined as at least two SBP >140 mmHg within the 2 years preceding the study period. We will exclude all patients who are currently pregnant. The CDS will review lab data starting five years before the visit to determine whether the patient has CKD using the logic described above. If the patient has CKD, the CDS will search BP data starting one year before the visit to determine whether the patient has had at least two SBP > 140 mmHg.

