## VII. RISKS AND DISCOMFORTS

There are minimal risks to physicians or patients as a result of the intervention. For clinicians, there is a risk that the decision support and other tools could have unexpected adverse consequences such as creation of more work, unfavorable workflow issues, and overdependence on technology. Although important to consider, these risks are balanced by evidence suggesting the effectiveness of computerized clinical decision support to improve the quality of patient care. For patients, the risks are those that are typically undertaken in the receipt of general medical care. That is, it is conceivable that the intervention could result in a change in management (e.g., ordering more tests, referral), but in the case of chronic kidney disease this may in fact lead to a clinical benefit. There also is the possibility of psychological risk to patients associated with being labeled as having chronic kidney disease; however, this risk is outweighed by the potential benefits associated with better evaluation and treatment of the disease. Finally, there is a risk of overtreatment of hypertension which may cause hypotension or an acute decrease in kidney function. The intervention is delivered to the primary care physician, who will weigh the risk and benefit of treatment intensification. However, this risk is expected to be low since we only recommend treatment intensification within consensus guidelines.

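### The creatinine outcome counts patients already above 2.0 at entry, which dilutes the comparison bearing on acute kidney decline; eGFR and UACR also lack a baseline reference

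*Combined protocol and SAP*

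**What the plan says.** Section VI, Table 1 lists serum creatinine above 2.0 as a dichotomous secondary outcome, assessed monthly, with the metric "Proportion of patients with Creatinine > 2.0". It gives no unit, no exclusion of patients already above the threshold and no new-onset rule. The eGFR row reads "eGFR Continuous eGFR", and the metric in the UACR row is just "Urine Albumin to Creatinine Ratio"; both are taken at 6, 12 and 18 months.

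Other rows of the table do refer to the patient's starting point. Mean SBP is analysed as "Change from baseline", and the allergy row is limited to new events: "Proportion of patients with newly documented allergy due to adverse drug events".

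The CKD entry criterion (sections III and V, Aim 2 and 2a) is "defined as two prior eGFR 16-59" mL/min/1.73m², or two UACR values above 30 mg/g. There is no upper limit on creatinine. Section VII names the renal risk as "overtreatment of hypertension which may cause hypotension or an acute decrease in kidney function".

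No model is given for creatinine, eGFR or UACR. The only one named is the multilevel logistic regression for process measures in section II, Aim 2b.

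**The concern.** The risk named in section VII is a decline within a patient. The creatinine outcome is a level. A patient who enters above 2.0 and stays there counts as an event in either arm, so these patients add the same quantity to both proportions and pull their ratio towards 1.

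The creatinine and eGFR rows are the only entries in Table 1 that measure filtration, and the DSMB review list in section IX does not name creatinine. A diluted null result on creatinine could therefore be read as reassurance that the data do not give. For eGFR and UACR, comparing follow-up levels without the entry value leaves between-patient variation in the error term that a baseline covariate would remove.

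**Working it through.** The plan states no prevalence, event rate, power or effect size for these outcomes, so there is no figure to reproduce. What follows is illustrative.

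**Inputs from the documents.** N = 2,350 (section II, Aim 2a); 70% with follow-up around 6 months and 174 clusters randomized 1:1 within pairs (section IV). Followed: 2,350 × 0.70 = 1,645, or about 822 per arm. The 70% is not stated to be laboratory follow-up; it is used here as if it were.

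**Assumed inputs.** Share q above 2.0 at entry, all remaining above: 2% to 20%. New-onset risk among the rest: 3% control, 5% intervention (true RR 0.05/0.03 = 1.67). One comparison, not a monthly series.

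**Can entry and outcome overlap?** The CKD-EPI version and coefficients are not in the documents. Taking the 2009 (non-Black coefficient) and 2021 equations as assumptions, with creatinine in mg/dL, a creatinine of 2.0 corresponds to eGFR of about 29–43 in men and 22–32 in women aged 40–90. An eGFR of 16 corresponds to creatinine of about 2.7–4.5 at ages 40–80. On those assumptions the lower part of the entry range already meets the outcome.

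**Creatinine.** As written, p0 = q + (1−q) × 0.03, p1 = q + (1−q) × 0.05, and z = (p1−p0)/√{[p0(1−p0) + p1(1−p1)]/822}. For new onset, z = 0.02/√{[0.03×0.97 + 0.05×0.95]/[822(1−q)]}.

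Example, q = 10%: p0 = 0.127, p1 = 0.145, RR = 1.14, SE = 0.0169, z = 1.06. New onset: 822 × 0.9 = 740 per arm, SE = 0.0102, z = 1.97.

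| q | p0 v p1 | Apparent RR | Control events already present at entry (q/p0) | z as written | z new onset |
|---|---|---|---|---|---|
| 2% | 4.94% v 6.90% | 1.40 | 40% | 1.69 | 2.05 |
| 5% | 7.85% v 9.75% | 1.24 | 64% | 1.36 | 2.02 |
| 10% | 12.7% v 14.5% | 1.14 | 79% | 1.06 | 1.97 |
| 20% | 22.4% v 24.0% | 1.07 | 89% | 0.77 | 1.85 |

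**Clustering.** There are 1,645/174 = 9.45 followed patients per cluster. With an assumed ICC of 0.02 the design effect is 1 + 8.45 × 0.02 = 1.17. Dividing by √1.17 = 1.08, the as-written z for q = 5%, 10%, 20% becomes 1.26, 0.98, 0.71. For new onset the cluster size is 9.45(1−q), and z becomes 1.88, 1.83, 1.74.

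**eGFR.** With correlation ρ between baseline and follow-up, ANCOVA leaves 1−ρ² of the raw variance: 0.51 at ρ = 0.7 and 0.19 at ρ = 0.9. Raw levels therefore need 1/(1−ρ²) = 2.0 to 5.3 times the patients. With an assumed SD of 12.4 (43/√12, a uniform spread over 16–59), 822 per arm and no clustering, the difference detectable with 80% power is 1.71 mL/min/1.73m² on raw levels and 1.22 to 0.75 with ANCOVA. A true difference of 2 still has power 0.98, 0.90 or 0.77 on raw levels for SD 10, 12.4 or 15.

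**The case against.** Several stronger conclusions are tempting, and the documents do not support them.

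- A reader might infer that values abnormal at entry swamp any treatment effect. The share above 2.0 is not given, and section I says that 95% of CKD patients have early disease. That figure describes CKD in general and not this cohort, but it points to a minority.
- A reader might infer bias. Clusters are randomized within pairs, so prevalent cases are balanced in expectation. Pairs are matched on cluster size and prior blood pressure and not on renal function, so chance imbalance is possible, but that is sampling error.
- A reader might infer that UACR will be analysed untransformed, or that baseline adjustment is ruled out. Table 1 says only that the variable is continuous; the model is unspecified.
- A reader might infer that the trial cannot assess the kidney risk at all. eGFR is compared between randomized arms at three time points, and raw levels can detect a moderate difference. Table 1 files creatinine under secondary outcomes and does not call it a safety endpoint.

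Two objections bear on the remedy, and both stand. A new-onset threshold still misses a rise from 1.0 to 1.9, and a rise from 2.5 to 4.0 leaves the main count, so the patients already above 2.0 need their own change measure. Nor does the remedy make the comparison well powered: z of 1.85 to 2.02 means power of about 46% to 52% at two-sided 0.05, and with clustering at the assumed ICC every new-onset z for q of 5% to 20% is below 1.96. The gain is relative.

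None of this answers the core point. The table already uses a change metric and a new-event metric elsewhere, and the creatinine row has neither.

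**Conclusion.** The point holds as a loss of sensitivity for creatinine and of precision for eGFR and UACR. It rests on the wording of Table 1 and on the absence of a creatinine ceiling at entry. Its size rests on assumptions: the share above 2.0 at entry, the new-onset risks, the ICC, the eGFR SD and the baseline correlation. Over an entry share of 5% to 20%, a true risk ratio of 1.67 shrinks to between 1.24 and 1.07, and the expected z falls by roughly a third to more than a half (2.02 to 1.36; 1.85 to 0.77). Even at 2% the ratio falls to 1.40. For eGFR the cost is equivalent to 2.0 to 5.3 times the patients at ρ of 0.7 to 0.9. The definition should be changed before analysis; the trial's validity is not in question.

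**What to change.** In Table 1 and the analysis text:

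1. State the creatinine unit.
2. Define the event as new onset: creatinine above 2.0 among patients at or below 2.0 at the last pre-enrolment value.
3. Report patients already above 2.0 separately, using their change from baseline.
4. Analyse eGFR, and UACR on the log scale, with models that account for clustering and adjust for the last pre-enrolment value.
5. Fix in advance the look-back window for a baseline value and a rule for patients without one, for example a missing-value indicator in the eGFR and UACR models and a stated place for patients with no baseline creatinine.
6. Reconcile the two look-backs: section III refers to EHR data from the past 2 years, section V (Aim 2 and 2a) to five.

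The cost is small, since no new data are collected and the decision support already reads prior laboratory results to establish eligibility. It is not free. Entry by the eGFR route requires no UACR, and section I reports that only 40% of CKD patients in these clinics had a urine albumin test, so baseline UACR will be missing for many. Patients who enter by UACR alone may lack a recent creatinine, and under a long look-back the last value may be years old.

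### The monthly creatinine row is a fixed level inside the entry range with no baseline reference, so it is a diluted and misclassified measure of acute kidney decline

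*Combined protocol and SAP*

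**What the plan says.** Table 1 in VI. Biostatistical Analysis lists serum creatinine above 2.0 as a dichotomous secondary outcome for both arms, assessed monthly. Its metric is "Proportion of patients with Creatinine > 2.0". It gives no unit, does not restrict the count to new events, and does not set aside patients already above the level.

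Under Specific Aim 2 & 2a Procedures, CKD for entry is "defined as two prior eGFR 16-59" by CKD-EPI, "or two prior UACR >30mg/g". The albuminuria route carries no eGFR limit. III. Subject Selection gives the same CKD criteria. The stated patient exclusions are pregnancy ("We will exclude all patients who are currently pregnant") and prior contact through the pilot study. None concerns baseline creatinine.

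VII. Risks and Discomforts states that "there is a risk of overtreatment of hypertension which may cause hypotension or an acute decrease in kidney function".

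Two other rows of Table 1 are worded differently. The primary SBP row is measured as change from baseline, and the allergy row is limited to newly documented allergies. Table 1 also has a continuous eGFR row at 6, 12 and 18 months, with no stated reference to baseline.

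**The concern.** The renal risk that the protocol names is a change: "may cause hypotension or an acute decrease in kidney function". The only dichotomous kidney-function row in Table 1 is a level. If that level lies within the range that entry allows, the row errs in both directions. It counts stable patients who entered above it, and it does not count large declines that end at or below it.

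Patients counted at entry add the same expected number to both arms. They pull the risk ratio towards 1 and add variance. Declines that stay at or below 2.0 remove true events. Either way, a comparison of arms on this row would be less sensitive to the harm that it appears meant to track.

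**Working it through.** The protocol gives no event rate, significance level or power for this row, so there is no planned figure to reproduce. The check has three steps.

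**1. Where creatinine 2.0 falls in the entry range.** The protocol names CKD-EPI without version or coefficients. I assume mg/dL and the 2009 equation, for creatinine above κ:

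eGFR = 141 × (Cr/κ)^−1.209 × 0.993^age (× 1.018 for women; × 1.159 with the race coefficient), with κ = 0.9 for men and 0.7 for women.

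- Man aged 70: 141 × (2.0/0.9)^−1.209 × 0.993^70 = 141 × 0.381 × 0.612 = 32.8.
- Woman aged 70: 141 × (2.0/0.7)^−1.209 × 0.993^70 × 1.018 = 141 × 0.281 × 0.612 × 1.018 = 24.7.
- Ages 50-80: 31-38 in men and 23-28 in women; 36-44 and 27-33 with the race coefficient.
- Ages 40-80, using either the 2009 equation without the race coefficient or the 2021 equation: about 31-43 in men and 23-32 in women.

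All these values lie inside 16-59. At eGFR 16, creatinine is about 3.4-4.5 in men and 2.7-3.5 in women, so every such patient enters above 2.0.

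**2. What the row does with individual patients (2009 equation).**

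- A man aged 70, stable at creatinine 2.3 (eGFR 28), is counted whenever creatinine is measured, with no change in his kidneys.
- A woman aged 70 goes from 1.0 to 1.9 (eGFR 57 to 26). She has lost (57 − 26)/57 = 54% and is not counted in this row.
- A patient entering at eGFR 59 can lose about 31-48% (men) or 48-61% (women) of eGFR, ages 40-80, and still be below 2.0.
- An albuminuria-route patient whose creatinine doubles from 0.8 to 1.6 is not counted.

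This step needs no assumed event rate.

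**3. Illustration of the dilution.** Assumptions: new events in 2% v 4% of patients not already above 2.0, all of them crossing 2.0; 2,350/2 = 1,175 per arm; everyone measured; two-sided 0.05; no clustering. With p the share above 2.0 at entry, the observed rates are p + (1 − p) × 0.02 and p + (1 − p) × 0.04. Power is Φ[(d − 1.96 × SE0)/SE1], where d is the difference in rates and SE0 and SE1 are the pooled and unpooled standard errors.

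For p = 10%, as written: 0.10 + 0.90 × 0.02 = 11.8% and 0.10 + 0.90 × 0.04 = 13.6%. The ratio is 1.15, d = 0.018, SE0 = SE1 = 0.01373, z = (0.018 − 0.0269)/0.01373 = −0.65, and power is 26%.

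For p = 10%, new crossings only: 1,175 × 0.90 = 1,057.5 per arm, 2% v 4%, SE0 = 0.00742, SE1 = 0.00741, z = (0.020 − 0.01454)/0.00741 = 0.74, and power is 77%.

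| Above 2.0 at entry | Rates as written | Risk ratio as written | Power as written | Power, new crossings only |
|---|---|---|---|---|
| 5% | 6.9% v 8.8% | 1.28 | 40% | 79% |
| 10% | 11.8% v 13.6% | 1.15 | 26% | 77% |
| 15% | 16.7% v 18.4% | 1.10 | 19% | 75% |

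The right-hand column is a best case. At p = 10%:

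- If only half of declines cross 2.0 (1% v 2%), new crossings have about 47% power and the row as written about 10%.
- If creatinine is available in 70% of patients, the follow-up share that IV. Subject Enrollment gives for around 6 months, the contrast is about 19% v 62%.

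Clustering would lower all of these.

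**The case against.** **The row is not labelled a safety outcome, and no test is stated for it.** Both are true. A monthly level could be plain surveillance. That it serves as the harm measure is an inference: it shares the monthly schedule with SBP below 110, the potassium limits and new allergy, and it is the only dichotomous kidney-function row matching the stated risk. The power figures are therefore illustrations and not a property of a planned test.

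**The eGFR row covers kidney function.** In part. A sustained fall from 57 to 26 would enter that comparison. But the row is assessed at 6, 12 and 18 months, is not stated as change from baseline and counts no events. A transient decline can fall between assessments, and a few large declines barely move a mean.

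**Randomisation balances the prevalent cases.** In expectation it does, across 174 clusters. In the 10% case the risk difference is 1.8 points against 2.0, so it hardly moves. A reader might infer that an uneven spread of advanced CKD would bias the result. Such chance imbalance is ordinary sampling error; what stands is dilution and lost precision.

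**The baseline share above 2.0 is unknown.** This stands. The documents do not give it, and albuminuria-route patients with normal creatinine would lower it. The direction is the same at every share tried.

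**Conclusion.** The concern holds as a defect in the definition of one secondary row. Followed literally, the row counts some stable patients as events and does not count some large declines. That rests on the protocol's wording together with the assumed CKD-EPI coefficients and mg/dL, and it holds across the ages, sexes and equation versions tried. The size rests on assumed event rates and an assumed baseline share: for 5-15% above 2.0 at entry, a true risk ratio of 2.0 appears as 1.28 to 1.10.

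A reader might go further and infer that the trial would miss kidney harm altogether. The documents do not support that. The eGFR row would show part of any sustained decline, and IX. Monitoring and Quality Assurance sends reported adverse events and deaths to the DSMB independently of this row, although it does not name creatinine.

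A reader might also extend the point to the two potassium rows, which are levels without a baseline too. Their limits are not built into eligibility and nothing in the documents sizes the effect, so they are not part of this finding.

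**What to change.** In Table 1, redefine the row as a new event relative to the patient's last creatinine before the enrolment visit, in two parts:

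- first creatinine above 2.0 among patients at or below 2.0 at baseline;
- a relative rise from the patient's own baseline, for all patients with a baseline value, with the threshold fixed before the data are seen.

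State the unit. Keep the level-based proportion as description only. Analyse the eGFR row as change from baseline or adjusted for baseline. The same not-already-outside condition for the potassium rows is optional.

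The cost is Table 1 wording and one derivation from EHR laboratory data that the eligibility logic already searches over five years. Patients entering by eGFR have at least two prior values. The downside is that patients above 2.0 at entry leave the first part, and patients with no prior creatinine leave both.

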## II. SPECIFIC AIMS

**Hypothesis:** The mean systolic blood pressure of the CKD population can be decreased by an intervention with three innovative features: 1) methods to synthesize EHR data in order to identify under-diagnosed chronic conditions, 2) iterative improvement in CDS content through human factors methods to maximize the “informativeness” of the CDS, and 3) the use of behavioral economic principles to create behavioral “nudges” internal and external to the CDS.

**Specific Aim 1:** To develop and validate the intervention.

**Specific Aim 1a:** To develop and validate the CDS that will: 1) synthesize existing laboratory tests, medication orders, and vital sign data; 2) increase recognition of CKD, 3) increase recognition of uncontrolled HTN in CKD patients; and 4) deliver evidence-based CKD and HTN management recommendations.

**Specific Aim 1b:** To improve the design and content of the CDS using human factors methods, specifically usability testing.

**Specific Aim 1c:** To develop a “wrap-around” intervention including two behavioral “nudges”: 1) pre-checked default orders, and 2) an email to obtain commitment from PCPs to obtain their commitment to follow the CDS recommendations.

**Specific Aim 2:** To test the effectiveness of the intervention.

**Specific Aim 2a:** To evaluate whether the intervention developed in Aim 1 significantly decreases mean systolic blood pressure in a population of CKD patients with blood pressure  $> 140/90$ ,  $N=2,350$  ( $N$  derived from EHR data about primary care patients at 15 clinics). We will evaluate the effectiveness of the intervention in a pragmatic, cluster-randomized controlled trial, randomized at the level of the physician (185 PCPs). Secondary outcomes will include hypertension-specific process measures, such as treatment intensification.

**Specific Aim 2b:** To evaluate whether the intervention improves process measures for quality of CKD care including: documented CKD diagnosis, annual serum creatinine test, and annual urine albumin test. We will also examine process measures related to CKD care. We will use multivariable logistic regression to account for clustering by PCP using a multilevel statistical regression model, as implemented in the SAS package through the GLIMMIX procedure.

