### IV. SUBJECT ENROLLMENT

Randomization and Enrollment: This study will utilize a matched-pair cluster randomized design with the intervention on the cluster level, and the main outcome (6 month minus baseline change in SBP) measured at the patient level. We will have 174 clusters (made up of 185 clinicians) in the study. We will match pairs of clusters with similar number of patients and prior year mean blood pressure of patients in the cluster. One cluster in each pair will be randomized to the intervention and unit one to usual care. Patients will be electronically identified and included in the study over the course of 12 months. Patients seen by PCPs during the pilot study will be excluded. Retrospective data indicates that 70% of patients have a follow-up around 6 months. Outcomes assessment will occur at 180 days (+/- 60 days). After the 12-month enrollment period ends, data collection will continue for 6 months so that those enrolled toward the end of the enrollment period will have a full 6 months to complete any interventions ordered by the PCP. A small subset of PCPs will be enrolled in a pilot study for approximately one month, as described below in study procedures Aim 1b. Clinical outcomes will be recorded and reviewed every month over the course of the trial.

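### Table 1 compares eGFR as a follow-up level with no stated baseline adjustment, which gives up precision that eGFR values already in the record could recover

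*Combined protocol and SAP*

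**What the plan says.** Section VI, Table 1 has an analysis-metric column. The primary row reads "Mean SBP Continuous Change from baseline 6 months, 12 months, 18 months". The eGFR row reads "eGFR Continuous eGFR 6 months, 12 months, 18 months", so its metric is the variable itself. The other continuous kidney row has the same form: "Urine Albumin to Creatinine Ratio Continuous Urine Albumin to Creatinine Ratio 6 months, 12 months, 18 months".

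Section VI gives no test, model or covariate for any continuous outcome. The only regression named is a multilevel logistic model, under Specific Aim 2b in Section II, for process measures.

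Prior kidney laboratory values are part of eligibility. Under Specific Aim 2 & 2a Procedures, CKD means "two prior eGFR 16-59 mL/min/1.73m 2 separated by 90 days, as calculated by CKD-EPI, or two prior UACR >30mg/g", and "The CDS will review lab data starting five years before the visit to determine whether the patient has CKD". A patient who enters by the eGFR route therefore has at least two earlier values on record. A patient who enters by the UACR route may have none, and that route sets no eGFR limits.

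On the design, Section IV says "We will have 174 clusters (made up of 185 clinicians) in the study" and "One cluster in each pair will be randomized to the intervention and unit one to usual care". Pairs are formed on cluster size and the previous year's mean blood pressure. eGFR is not a matching factor.

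**The concern.** Patients can enter with an eGFR anywhere from 16 to 59, or outside that range by the UACR route. Part of the spread in eGFR at follow-up is therefore spread that was already there at entry. A comparison of follow-up levels leaves all of it in the error term, although the earlier values needed to remove it are in the record.

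Two things are at stake. The first is precision on kidney function. Section VII names an acute fall in kidney function as a risk of overtreatment, and Section VIII hopes that better care will ultimately prevent disease progression. The second is that a chance difference between arms in baseline eGFR is left in the point estimate, since neither the matching nor a stated covariate deals with it.

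The silence also leaves the choice between a raw, a change-score and an adjusted analysis open until the data are seen.

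**Working it through.** The plan states no power, alpha, SD, ICC or effect size for eGFR, so there is no figure of its own to reproduce. The sample size of 2,350 in Section II is a count, "derived from EHR data about primary care patients at 15 clinics", not the result of a power calculation.

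**Inputs from the plan**
- Patients: 2,350 (Section II). Clusters: 174, one of each pair to each arm (Section IV).
- Follow-up near 6 months: 70% (Section IV). This is a follow-up rate, not a rate of eGFR measurement, so 2,350 × 0.70 = 1,645 is an upper bound, or 822.5 per arm.
- Mean cluster size among those followed: 1,645 / 174 = 9.45.

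**Assumptions**
- Two-sided alpha 0.05 and 80% power, so the multiplier is 1.96 + 0.84 = 2.80.
- SD 10 to 12.4. The upper value is the SD of a uniform spread over 16 to 59: 43 / √12 = 12.4.
- ICC 0.01 to 0.05. Correlation rho between baseline and follow-up 0.5 to 0.8.
- The same design effect for raw and adjusted analyses. Any gain from pair matching is ignored.

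**Step 1. Design effect.** DE = 1 + (9.45 − 1) × ICC = 1.08 at ICC 0.01 and 1.42 at ICC 0.05.

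**Step 2. Raw level.** Detectable difference = 2.80 × SD × √(4 × DE / 1,645).
- SD 10, ICC 0.01: 1.44.
- SD 12.4, ICC 0.05: 2.04.

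**Step 3. Adjusted for baseline.** The residual variance is SD² × (1 − rho²), so the detectable difference is multiplied by √(1 − rho²).

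| rho | Variance removed | Multiplier | Detectable difference, mL/min/1.73 m² |
|---|---|---|---|
| raw level | 0% | 1.00 | 1.44 to 2.04 |
| 0.5 | 25% | 0.87 | 1.25 to 1.77 |
| 0.8 | 64% | 0.60 | 0.86 to 1.23 |

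The share of variance removed depends on rho alone, not on SD or sample size.

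**Step 4. Power for fixed differences** (SD 12.4, ICC 0.02, DE 1.17).

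| True difference | Raw | Adjusted, rho 0.5 | Adjusted, rho 0.8 |
|---|---|---|---|
| 1 mL/min/1.73 m² | 33% | 41% | 71% |
| 2 mL/min/1.73 m² | 86% | 94% | >99% |

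**Step 5. A wider spread.** The UACR route sets no eGFR limits, so the SD may exceed 12.4. At SD 20 and ICC 0.02 the detectable difference is 2.99 raw and 1.79 at rho 0.8. Power for 2 mL/min/1.73 m² is 47% and 88%.

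**Step 6. Would a change score, as for SBP, do as well?** Its variance is 2 × (1 − rho) × SD². At rho 0.5 that equals SD², no gain over the raw level. At rho 0.8 it is 0.40 × SD², against 0.36 × SD² after adjustment. It is never more precise than adjustment.

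These figures are for 6 months. Data collection stops 6 months after enrolment closes, so fewer patients can reach 12 or 18 months, and detectable differences there will be larger.

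**The case against.** The strongest reply is that Table 1 names measures, not models. The metric cell repeats the variable name for eGFR and for UACR, and Section VI gives no model for SBP either. Silence does not rule out a baseline covariate. This is right as a reading: the plan leaves adjustment unstated and does not exclude it. But the same column does distinguish a change from a level, and the literal reading for eGFR is the level.

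A reader might go further and infer that between-patient spread hides any effect on kidney function. The plan's own numbers do not support that. At SD 10 to 12.4 the raw comparison can detect about 1.4 to 2.0 mL/min/1.73 m², and in Step 4 it has 86% power for a difference of 2. Effects near 1 are the ones likely to be missed. Nor is the raw comparison biased: randomization protects it in expectation, and its confidence interval already allows for chance imbalance.

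The size of the gain is also open to challenge. Qualifying values may be up to five years old, and no recent eGFR is required, so rho may be low. At rho 0.5 the detectable difference shrinks by only 13%. To say that most of the variance is known at entry needs rho above 0.71, which the plan does not give. This stands, and it is why the result is given as a range.

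Finally, the alert offers laboratory orders, so who has a follow-up eGFR may differ by arm. That is a separate matter which baseline adjustment does not cure. Serum creatinine above 2.0 has its own monthly row, so eGFR is not the only kidney measure, but that row is a threshold status with no baseline either.

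**Conclusion.** The point holds as a loss of precision on a secondary outcome. The plan lists eGFR as a follow-up level, states no baseline adjustment, and does not use earlier values that it already reads. Adjustment would remove 25% of the variance at rho 0.5 and 64% at rho 0.8. The 80%-power detectable difference would fall from about 1.4-2.0 to 1.25-1.8 or 0.9-1.2 mL/min/1.73 m² respectively.

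This rests on assumed rho, SD and ICC and on 1,645 patients having an eGFR near 6 months, which is the most the plan's follow-up rate allows. An old baseline would lower rho and the gain; a wider SD would raise all the detectable differences in proportion. The finding does not extend to bias in the raw comparison, or to its being unable to detect effects of moderate size.

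**What to change.** In Table 1, change the eGFR metric to follow-up eGFR adjusted for the last eGFR before the enrolment visit. In Section VI, write out the analysis: a linear mixed model with arm, baseline eGFR and matched pair, and a random effect for PCP cluster, reporting the adjusted mean difference and its confidence interval. State how far back a value may lie and still count as baseline. Do the same for UACR on the log scale. Adjustment is preferable to copying the SBP row's change score, for the reason in Step 6.

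The cost is small. No new data are needed, but it takes more than one table line, because the plan's only named model is logistic and cannot be cited for a continuous outcome. Patients with no earlier eGFR, possible on the UACR route, need a missing-baseline indicator so that they stay in the analysis.
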